#### **9.6.3            Laboratory Test Results**

The following analyses will be provided for chemistry, hematology and urinalysis laboratory data:

- Shifts tables of the laboratory toxicity for all laboratory parameters based on CTCAE grade (version 4.03) relative to baseline will be tabulated by body weight cohort and treatment group. In the cases when CTCAE grading scales include numeric ranges in combination with clinical assessment (eg, Potassium [Hypokalemia]), laboratory test results may be summarized based on standard normal ranges or by CTCAE grade utilizing investigator's input.
- Descriptive statistics of change from baseline by visit for all laboratory parameters
- Subject listing of grades  $\geq 3$  laboratory toxicities for all laboratory parameters as applicable
- Subject incidence of suspected Hy's Law cases
- Summary of liver function abnormalities for alanine aminotransferase (ALT), aspartate aminotransferase (AST), alkaline phosphatase (ALP), and total bilirubin (TBL) or the following categories:
  - ALT ( $> 3x$  upper limit of normal (ULN);  $> 5x$  ULN;  $> 10x$  ULN;  $> 20x$  ULN respectively)
  - AST ( $> 3x$  ULN;  $> 5x$  ULN;  $> 10x$  ULN;  $> 20x$  ULN respectively)
  - AST or ALT ( $> 3x$  ULN;  $> 5x$  ULN;  $> 10x$  ULN;  $> 20x$  ULN respectively)
  - Total Bilirubin ( $> 1x$  ULN;  $> 1.5x$  ULN;  $> 2x$  ULN respectively) and ALP ( $> 1.5$  ULN)

Unscheduled assessments will be incorporated in the laboratory analyses where possible.

#### **9.6.4            Vital Signs**

Vital signs will be reviewed for each subject. Summaries of heart rate, temperature, and blood pressure (systolic and diastolic) data over time and change from baseline will be provided.

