## 9. SAFETY DATA COLLECTION, RECORDING, AND REPORTING

### 9.1 Definition of Safety Events

#### 9.1.1 Adverse Events

An adverse event is defined as any untoward medical occurrence in a clinical trial subject. The event does not necessarily have a causal relationship with study treatment. The Investigator is responsible for ensuring that any adverse events observed by the Investigator or reported by the subject are recorded in the subject's medical record. The definition of adverse events includes worsening of a pre-existing medical condition. Worsening indicates that the pre-existing medical condition or underlying disease (eg, diabetes, migraine headaches, gout) has increased in severity, frequency, and/or duration more than would be expected and/or has an association with a significantly worse outcome than expected. A pre-existing condition that has not worsened more than anticipated (eg, more than usual fluctuation of disease) during the study, or involves an intervention such as elective cosmetic surgery or a medical procedure while on study, is not considered an adverse event.

The Investigator's clinical judgment is used to determine whether a subject is to be removed from treatment due to an adverse event. In the event a subject, or subject's legally acceptable representative requests to withdraw from protocol-required therapies or the study due to an adverse event, refer to Section 8.1 for additional instructions on the procedures recommended for safe withdrawal from protocol-required therapies or the study.

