##### **10.4.2.3 Safety Endpoints**

###### **10.4.2.3.1 Vital Signs**

Vital signs will be reviewed for each subject. Summaries of heart rate and blood pressure data over time and change from baseline will be provided. Depending on the extent and scope of change in other vital signs, summaries of other vital signs may be provided.

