### 3.2 Sample Size

The study population will consist of 2 cohorts based on body weight enrolling a total of at least **52** subjects up to approximately 60 subjects in the study. Cohort 1 will enroll at least **12** subjects and up to approximately 22 subjects in total with body weight of < 40 kg at baseline. It is anticipated that most subjects in this cohort will be 6 to < 12 years of age. Cohort 2 will enrol at least 35 subjects and up to approximately 38 subjects with a body weight of  $\geq$  40 kg at baseline. It is anticipated that most subjects in this cohort will be 12 to < 18 years of age.

Subjects weighing < 40 kg (Cohort 1) will receive a dose of 35 mg or 70 mg for a total of at least **12** and up to approximately **15** subjects completing Week 12 assessments.

Subjects weighing  $\geq$  40 kg (Cohort 2) will receive a dose of 70 mg or 140 mg for a total of at least 26 and up to approximately 30 subjects completing Week 12 assessments.

The rate of early discontinuation up to Week 12 assessments is assumed to be 20% and similar across the two cohorts.

All subjects in this study will be administered AMG 334. The sample size for this study is based on clinical and practical considerations to adequately fulfil its objectives and to inform on planned phase 3 pediatric studies. Assuming clearance (CL) and central volume of distribution (Vc) on body weight basis is similar between pediatric subjects and adults, and assuming the percentage coefficient of variation for CL and Vc are 43% and 53%, respectively (based on total between-subject-variability from adult population PK), the proposed sample size provides > 80% power to estimate 95% confidence interval (CI) of CL and Vc within 60-140% of the true parameters for both weight cohorts combined and across the two age categories ([Wang Y et al, 2012](#)).

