## 7.2 Primary Analysis

**The primary analysis for the study will be performed at the End of the Study milestone described in the protocol Section 3.5.2. All data will be cleaned and a database lock will occur.**

No formal hypothesis testing will be performed; all analyses will be descriptive. PK and safety data will include summaries by body weight cohort and AMG 334 treatment dosage group. **Primary analysis will include safety summaries for ITP only. Safety data will be analyzed by GBS and PK data will be analyzed by CPMS.** The review of the results of this primary analysis will inform on further pediatric studies utilizing AMG 334.

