## 9. Statistical Methods of Analysis

### 9.1 General Considerations

Unless otherwise stated, descriptive statistics will be provided for demographic and baseline characteristic by body weight cohort (< 40 kg and  $\geq$  40 kg), treatment dosage (35 mg, 70 mg and 140 mg), and all subjects combined.

Safety summaries during the **entire study, ITP or OEP, as applicable**, will be provided by body weight cohort (< 40 kg and  $\geq$  40 kg), treatment dosage (35 mg, 70 mg and 140 mg), and all subjects combined.

Where appropriate, **safety** summaries **will be provided by** each age group (adolescents and children) separately.

PK data will be summarized by body weight cohort and treatment dosage.

Descriptive statistics on continuous measurements will include **number of subjects (n)**, means, medians, standard deviations (and standard errors for post-baseline data), first and third quartiles, and minimum and maximum, while categorical data will be summarized using frequency counts and percentages. No formal statistical hypothesis testing will be performed.

When data are summarized by visit, the values recorded against the scheduled visits, including any time windows specified in the protocol will be used.

When assessing post-baseline minimum/ maximum increases or decreases over the study (**eg, shift in lab toxicity grade**), all assessments, including unscheduled assessments will be used.

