### 10. Changes From Protocol-specified Analyses

As a change from protocol-specified analysis per protocol amendment 4 dated 20 March 2020, an unplanned interim analysis was conducted in May 2021, when at least 8 children (aged 6 to < 12 years) had completed study Week 12 assessments, to facilitate engagement with health authorities regarding modifications to the AMG 334 Pediatric Investigational Plan (PIP) and commencement of enrollment of children in AMG 334 Pediatric Phase 3 studies. An as-is database snapshot occurred and included all data up to and including corresponding data cutoff date. Safety analyses including AEs, vital sign, laboratory, ECG, [REDACTED] was summarized by GBS group. PK data was analyzed by CPMS group based on all available PK data including all adolescent and children subjects from both Cohort 1 (< 40 kg) and Cohort 2 ( $\geq$  40 kg).

The unplanned interim analysis fulfilled the requirement of second interim analysis (as described in [Section 7.1](#)), as reflected in Protocol Amendment 5 dated 03 November 2021. All TFLs generated during the unplanned interim analysis will be considered as second interim analysis outputs for the purpose of study documentation.

There is a change in timing of the primary analysis (as described in [Section 7.2](#)) compared to the Protocol Amendment 5 dated 03 November 2021.

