**14. Appendices**

**Appendix A. Reference Values/Toxicity Grades**

Adverse event severity and laboratory toxicity are graded based on National Cancer Institute (NCI) Common Toxicity Criteria version 4.03 or higher, which is available at the following: [https://evs.nci.nih.gov/ftp1/CTCAE/CTCAE\\_4.03/CTCAE\\_4.03\\_2010-06-14\\_QuickReference\\_5x7.pdf](https://evs.nci.nih.gov/ftp1/CTCAE/CTCAE_4.03/CTCAE_4.03_2010-06-14_QuickReference_5x7.pdf)

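### Blood pressure is part of a primary safety endpoint in subjects aged 6 to <18 years, but no planned table counts those whose measured pressure becomes high for age, sex and height

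*SAP*

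**What the plan says.** Protocol 10.1.1 and SAP 2.1 make change in vital signs part of a primary endpoint. The population is aged 6 to <18 years.

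The analysis is in SAP 9.6.4. It opens with a review of each subject's vital signs, for which no criterion, count or listing is given, and continues: "Summaries of heart rate, temperature, and blood pressure (systolic and diastolic) data over time and change from baseline will be provided". Protocol 10.4.2.3.1 has the same structure: "Summaries of heart rate and blood pressure data over time and change from baseline will be provided". SAP 5.6 defines change as a simple difference. For continuous data SAP 9.1 gives n, mean, median, SD and standard error, plus "first and third quartiles, and minimum and maximum". SAP Table 9-1 asks only for summary statistics by weight cohort and dose. SAP 9.1 adds safety summaries by age group where appropriate, and SAP 4.2 makes selected age-group analyses optional.

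SAP Appendix A confines grading to two kinds of data: "Adverse event severity and laboratory toxicity are graded based on National Cancer Institute (NCI) Common Toxicity Criteria version 4.03 or higher". Nothing in either document sets a blood-pressure category, cut-off, percentile or count.

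Protocol 7.2.4 has children measured in the right arm because that is where normative values come from. No analysis then uses normative values.

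**The concern.** Between 6 and 18 years the same pressure in mmHg can be ordinary for one subject and high for another, because the limit depends on age, sex and height. A mean change and a largest change do not say whether anyone crossed their own limit, or how many did.

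The plan treats the neighbouring components differently. Laboratory data get grade shift tables, a listing of grade 3 and above, and liver-threshold counts (SAP 9.6.3). ECG gets a shift in diagnosis (9.6.6). Neurological assessment gets incidence of abnormality (9.7.3). Vital signs alone have no categorical output.

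At stake is how easily one primary safety component can be read in the primary and final analyses. SAP 7.2 says of the former: "The review of the results of this primary analysis will inform on further pediatric studies utilizing AMG 334".

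**Working it through.** The plan states no figure to reproduce. The checks ask whether the planned outputs can yield the count, and how a count would behave.

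**1. Can the count be recovered from the planned statistics?** Take n = 12, the Cohort 1 minimum. Assume 12 systolic values (98 to 121 mmHg) and 12 subject-specific limits (104 to 126 mmHg); neither set comes from the documents. The planned statistics are mean 109.8, median 110.0, SD 7.5, Q1 104.5, Q3 115.5, minimum 98, maximum 121. Matching the same values to the limits in different ways puts between 0 and 9 subjects at or above their own limit. The statistics do not change, so the count cannot be recovered.

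**2. Does the maximum change stand in for it?** Assumed model: z = √ρ·u + √(1−ρ)·e, with u the subject effect and e the reading error (both standard normal), ρ = 0.5 to 0.8, and the limit at the 95th percentile (z = 1.645). A new crossing is baseline below the limit and the visit at or above it. There is one post-baseline visit and no drug effect. Arm sizes follow from the allocation ratios: Cohort 1 at 12 gives 4 and 8; Cohort 2 at 35 gives 7 and 28.

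| Arm size | Largest-change subject is one who crossed, given at least one crossing | Two or more crossed, given at least one |
|---|---|---|
| 28 | 27-36% | 31-44% |
| 8 | 50-56% | 9-13% |
| 4 | 69-74% | 4-6% |

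In the large arm the biggest rise usually belongs to a subject who started low, not to one who crossed.

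**3. What would a count show by chance?** This uses the same model, restricted to baseline below the limit, systolic only. The result depends on which readings count. One reading at each of four visits corresponds to Days 29, 57, 85 and 169. Protocol 7.2.16 also requires a 30-minute post-dose reading at dosing visits and a 2-hour reading on Day 1. A subject who does not enter the extension then has 2 (Day 1) + 2 (Day 29) + 2 (Day 57) + 1 (Day 85) + 1 (Day 169) = 8 post-baseline readings.

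| Readings counted | Any elevation | Two consecutive visits |
|---|---|---|
| One at each of 4 visits | 7-12% | about 2% |
| All 8, visit elevated if any reading is | 10-19% | about 3-4% (2.8-4.3%) |

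I re-ran both rows and they reproduce. For scale, if all 52 subjects followed that schedule, any elevation by chance would be 52 × 0.07 = 3.6 to 52 × 0.12 = 6.2 subjects in the first case and 52 × 0.10 = 5.2 to 52 × 0.19 = 9.9 in the second.

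**4. What could a count detect?** Assume a sustained 15 mmHg rise and SD 10 to 12 mmHg, so a shift of 15/10 = 1.5 to 15/12 = 1.25 SD, with one reading at each of four visits. Detection probability is 0.50-0.74 for any elevation and 0.30-0.41 for two consecutive visits. With zero cases, the exact 95% upper bound is 1 − 0.025^(1/n): 36.9% for n = 8, 12.3% for n = 28, 6.8% for n = 52.

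**The case against.** The strongest reply is that the plan already looks at individuals. SAP 9.6.4 and Protocol 10.4.2.3.1 both begin with review of each subject, so a reader who inferred that the plan offers nothing beyond raw averages would be wrong. Other outputs help too. Minimum and maximum reveal a large individual rise. Age-group summaries are foreseen. The weight cohorts partly separate the ages; of Cohort 1 SAP 3.2 says: "It is anticipated that most subjects in this cohort will be 6 to < 12 years of age". Protocol 9.1.1 is broad ("An adverse event is defined as any untoward medical occurrence in a clinical trial subject"), so elevation that an investigator reports reaches the AE tables with a CTCAE grade.

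All of that stands, and it narrows the point. What remains is that the review has no criterion and no tabulated result, that AE tables count reports and not measurements, and that two age bands or two weight cohorts still mix years of growth and both sexes.

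A second reply is that the added table performs modestly: limited sensitivity, no untreated control, nearly uninformative small arms, and a count that could be derived later from collected data. This also stands. It is why the point is minor, and why the listing and the all-subjects column carry most of the value. Deriving the count later, however, means choosing the reference and the reading after the data are seen.

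A reader might also infer that Phase 3 dose selection was compromised. The documents do not support that. SAP 10 records that "an unplanned interim analysis was conducted in May 2021" and counts it as the second interim, so it precedes this SAP version of March 2022.

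**Conclusion.** The gap is real and minor. No planned table counts subjects whose measured pressure becomes elevated for age, sex and height, although the other components of the same primary endpoint have a shift table or an abnormality count. This follows from the text alone and needs no assumption. The sizes in the working do rest on assumptions: normal z-scores, equal correlation of 0.5 to 0.8, a 95th-percentile limit, SD 10 to 12 mmHg and a 15 mmHg rise. None of these is in the documents.

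Two stronger conclusions should not be drawn. The first is that a blood-pressure effect is being missed: the documents report no such signal, and history of hypertension is an exclusion (criterion 207). The second is that a single chance rate of 2% could be written into the SAP as a benchmark. That figure holds only for one reading per visit, and a worst-reading table over all scheduled readings would give about 3-4%.

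**What to change.** Keep the raw summaries and add to SAP 9.6.4, before database lock:

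- One descriptive shift table, baseline category to worst post-baseline category, for systolic and diastolic pressure, against a named paediatric reference for age, sex and most recent height.
- A rule for the reading that counts at each visit: pre-dose at dosing visits. Without it, the SAP 9.1 rule that post-baseline extremes use all assessments would bring in post-dose and unscheduled readings.
- A listing of affected subjects that marks elevation at two consecutive visits.
- Display for all subjects, age group, weight cohort and dose, with a note that counts are uncontrolled and that arms of 4 to 8 say little. State no fixed chance rate.

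The cost is SAP wording, one derived variable for each pressure, one table and one listing, all from data already collected. The downsides should be stated. Height is scheduled only at screening and the final visit, so mid-study categories use an old height. Readings are supine and may not match the reference; a shift from the subject's own baseline category reduces this problem but does not remove it. There is no untreated control.

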#### **9.6.5            Physical Measurements**

[figure not shown]
Height, weight, and BMI will be summarized by visit and change from baseline will be provided, as applicable.

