The proposed dosing strategy in this study is expected to confirm that the PK profile of equivalent doses of AMG 334 in either cohort of pediatric subjects of both age categories combined (ie, 35 or 70 mg for subjects weighing < 40 kg, and 70 or 140 mg for those weighing ≥ 40 kg, respectively) is similar to that previously established in adults receiving either 70 mg or 140 mg. Body weights of the younger age group are expected to be roughly 50% of the older age group, the latter of which overlaps with adult body weights according to the US Centers for Disease Control (CDC NHANES 2009-2010). Children with a body weight < 18 kg are excluded from this study. The fifth percentile of body weight in 6-year old males is 19.5 kg and in 6-year old females is 18.4 kg, thus the body weight range in this study encompasses the 6-year old population (Diamond McDowell et al, 2008).

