### **7.2.15 Screening and Enrollment**

The following procedures are to be completed during the screening period at time points designated in the Schedule of Activities ([Table 1](#) and [Table 2](#)).

- Confirmation that the Informed Consent Form and Assent form have been signed
- Demographic data including sex, age, race, and ethnicity will be collected in order to explore their possible association with subject safety and treatment effectiveness. Additionally demographic data will be used to study the impact pharmacokinetics of the protocol-required therapies
- Physical Examination as per standard of care
- Neurological Examination
- Medical and Surgical History
- Single 12-Lead ECG
- Height and Weight
- Vital signs (eg, blood pressure, heart rate temperature)

- Laboratory Assessments:
  - Chemistry Panel
  - Hematology Panel
  - Urinalysis
  - Estimated Creatinine Clearance
  - Serum Pregnancy Test (female subjects of reproductive potential)
  - Drug and Alcohol screen (adolescents only; at Investigator's discretion for children)
  - Hepatitis serology testing
- Serious Adverse Event reporting
- Documentation of concomitant and rescue medications
- Patient Health Questionnaire (PHQ-A) (adolescents only)

Subjects who fail screening may be re-screened upon discussion with and approval by the Amgen Medical Monitor. A new informed consent and assent form must be signed unless it has been < 21 days since the previous ICF and assent signature was obtained.

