#### **7.2.16        Initial 12 Week Treatment Phase Visits**

The following procedures will be completed during the 12 week treatment phase at the times designated in the Schedule of Activities ([Table 1](#) and [Table 2](#)). All visits during this phase, except Day 1 are  $\pm$  3 days.

- Body weight pre-dose
- Neurological exam pre-dose
- Vital signs (eg, blood pressure, heart rate, temperature) pre-dose and 30 minutes post-dose; also 2 hours post-dose on Day 1 only.
- Physical examination pre-dose and 30 minutes post-dose.; also 2 hours post-dose on Day 1 only.
- Single 12-Lead ECG pre-dose and 2 hours post-dose on Day 1 only.
- Laboratory Assessments:
  - Chemistry Panel
  - Hematology Panel
  - Urinalysis
  - Urine Pregnancy Test (female subjects of reproductive potential)
  - Drug and Alcohol Screen

- Serious Adverse Event reporting
- Adverse Event reporting

- Modified PedMIDAS pre-dose
- Documentation of concomitant and headache rescue medications.
- Collect blood for biomarker development pre-dose
- Pharmacogenetics (optional) pre-dose

- AMG 334 serum PK collection pre-dose
- Study drug administration (dose will be based on pre-dose body weight collected on Day 1)
- Following the AMG 334 dose administration at Day 1, all subjects will be monitored at the facility for at least 2 hours post-dose, at which point they will be discharged with instructions to return to the research facility according to the procedures provided in the Schedule of Activities ([Table 1](#) and [Table 2](#)). Following the AMG 334 dose administration on Days 29 and 57, all subjects will be monitored at the facility for at least 30 minutes post-dose. The post dose safety monitoring will be extended to 2 hours if the subject showed any safety concerns post-dose during the last dosing visit.

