## 7.2.17 Optional 40-Week Extension Phase

The following procedures will be completed during the optional 40-week extension phase, for adolescents who choose to continue treatment, at the times designated in the Schedule of Activities ([Table 1](#) and [Table 2](#)). All visits during this phase are  $\pm$  4 days of the scheduled time point. Children 6 to < 12 years of age will not be offered the option to enter the optional 40-week extension phase.

- Confirmation that the Informed Consent Form [Appendix A](#) has been signed
- Body weight (pre-dose)
- Vital signs (eg, blood pressure, heart rate, temperature) (pre-dose)
- Physical examination (pre-dose)
- Laboratory Assessments:
  - Chemistry Panel
  - Hematology Panel
  - Urinalysis
  - Urine Pregnancy Test pre-dose (female subjects of reproductive potential)
- Serious Adverse Event reporting
- Adverse Event reporting

- Adverse Device Effect reporting
- Documentation of concomitant and headache rescue medications
- AMG 334 serum PK Sample (pre-dose)

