#### 7.2.18 End of Study Visit

All Subjects will be followed for 16 weeks after the last administration of AMG 334.

The following procedures will be completed during the final visit (Study Day 169, early termination or Day 449, if subject continued in the optional 40-week extension phase).

- Physical Examination as per standard of care
- Single 12-Lead ECG
- Height and Weight Measurements
- Vital signs (eg, blood pressure, heart rate, temperature)
- Laboratory Assessments:
  - Chemistry Panel
  - Hematology Panel
  - Urinalysis
  - Urine Pregnancy Test (female subjects of reproductive potential)
  - Drug and Alcohol Screen

- AMG 334 serum PK Sample
- Serious Adverse Event reporting
- Adverse Event reporting
- Adverse Device Effect reporting
- Documentation of concomitant and rescue medications

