**5.3 Study Points of Reference**

**Baseline**

Unless otherwise stated, baseline will be defined as the last assessment taken prior to the first AMG 334 administration (ie, Day 1 pre-dose or Screening if Day 1 pre-dose is not available) of the ITP. For subjects continuing treatment in an OEP after completion of the ITP, their baseline will be the same as the ITP.

For ECG and Neurological Evaluation, the entire set of data from the Day 1 visit will be used as baseline. If the data is missing on Day 1, the entire set of data from the Screening visit will be used as baseline.

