## 5.6 Arithmetic Calculations

### Change from Baseline:

The arithmetic difference between a post-baseline value and the baseline value:

- Change from Baseline = (Post-baseline Value – Baseline Value)
- Percent change from Baseline = [(Post-baseline Value – Baseline Value) / Baseline Value] x 100

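### Height, weight and BMI are summarised only as raw change from baseline in growing subjects, so the planned table mixes normal growth with any drug effect; the height to use for BMI is also unspecified

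*SAP*

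**What the plan says.** SAP 9.6.5 gives one sentence: "Height, weight, and BMI will be summarized by visit and change from baseline will be provided, as applicable". SAP 5.6 defines change from baseline as "The arithmetic difference between a post-baseline value and the baseline value", and also defines percent change. Neither document names a z-score, percentile, height velocity or growth reference for these measurements.

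Height is measured at two scheduled points:

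- **Screening.** Protocol 7.2.15 lists "Height and Weight".
- **Initial 12-week phase.** Protocol 7.2.16 lists "Body weight pre-dose" and no height.
- **Extension.** Protocol 7.2.17 again lists weight only. Table 2 shows weight at Weeks 12, 24, 36 and 48 and at safety follow-up, and height at safety follow-up only.
- **Final visit.** Protocol 7.2.18 lists "Height and Weight Measurements", at Day 169, Day 449 or early termination.

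Only adolescents may enter the extension (Protocol 7.2.17). Every subject receives AMG 334, with low and high dose randomised 1:2 below 40 kg and 1:4 at or above 40 kg (Protocol 3.1 and 5.1). SAP 9.1 reports safety by weight cohort, by dosage and for all subjects combined, with age-group summaries where appropriate.

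**The concern.** Most subjects in this age range will grow whether or not the drug affects growth. Without an untreated arm or an external growth standard, a mean gain in height or weight cannot be read as normal, slow or fast.

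The groups being tabulated also differ in expected growth. The 35 mg dose is given only below 40 kg and the 140 mg dose only at or above 40 kg. The heavier cohort is expected to be mostly adolescents, the only subjects who can be followed for 64 weeks. A raw-change column by dosage therefore carries differences in age and follow-up as well as dose.

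BMI raises a further question. A by-visit BMI summary is planned, but at intermediate visits only weight is scheduled. The SAP gives no BMI formula and no rule for the height to use. Baseline needs a rule too: SAP 5.3 takes the Day 1 pre-dose value and falls back on screening, so baseline weight comes from Day 1 while baseline height can only come from screening.

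What is at stake is whether a paediatric safety table can be interpreted. No test or primary endpoint is affected.

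**Working it through.** **1. Follow-up length, from the documents.** Protocol 3.5.1 gives up to 27 weeks without the extension (3 + 12 + 12 = 27) and up to 67 weeks with it (3 + 12 + 40 + 12 = 67). Both are reproduced. Counted from Day 1, the final visits fall at (169 − 1)/7 = 24 weeks and (449 − 1)/7 = 64 weeks. They also agree with the last dose plus 16 weeks: 57 + 112 = 169 and 337 + 112 = 449.

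**2. Raw height change from growth alone.** The growth rate g is an assumption; the documents give none. I use 1 to 7 cm/year and the full 3-week screening window.

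Height change = g × weeks from screening / 52

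| g (cm/year) | To Day 169 (27 weeks) | To Day 449 (67 weeks) |
|---|---|---|
| 1 | 0.5 cm | 1.3 cm |
| 4 | 2.1 cm | 5.2 cm |
| 7 | 3.6 cm | 9.0 cm |

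At any common growth rate, the longer follow-up gives 67/27 = 2.5 times the change, with no drug effect.

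**3. Whether the randomised dose contrast helps.** The enrolment limits and allocation ratios give about 4 v 8 to 7 v 15 subjects in Cohort 1 and 7 v 28 to 8 v 30 in Cohort 2. The difference detectable with 80% power at two-sided 5%, in SD units by the normal approximation, is (1.96 + 0.84) × √(1/n₁ + 1/n₂):

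- Cohort 1: 1.72 SD (4 v 8) to 1.28 SD (7 v 15)
- Cohort 2: 1.18 SD (7 v 28) to 1.11 SD (8 v 30)

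No such test is planned. The figures show only that the low v high comparison says little about growth. It also cannot show an effect common to both doses.

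**4. BMI if screening height were carried forward.** The SAP does not state this; it is a what-if. The screening height of 155 cm is assumed. Week 48 is 3 + 48 = 51 weeks after screening.

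Overstatement = ((155 + g × 51/52)/155)² − 1

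| g (cm/year) | Height at Week 48 | BMI overstated by |
|---|---|---|
| 1 | 155.98 cm | 1.3% |
| 4 | 158.92 cm | 5.1% |
| 7 | 161.87 cm | 9.1% |

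An adolescent who has stopped growing would show none. At the final visit height is measured again, so the error would vanish there.

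**5. What the SAP's general rules imply for BMI.** SAP 9.1 uses values recorded at scheduled visits, SAP 8.3 says missing data are in general not imputed, and SAP 9.6.5 ends with a qualifier limiting the summaries to where they apply. Together these permit BMI only where height was measured. That leaves one scheduled post-baseline BMI per subject, which sits awkwardly with a by-visit summary. Neither reading is written down.

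**The case against.** The strongest reply is that this is a supportive descriptive table. Height, weight and BMI are not among the listed primary safety endpoints (SAP 2.1), nothing is tested, and z-scores could be derived at reporting from data already held. The plan also deals with part of the mixing: summaries are by visit and by study phase, extension data have their own analysis set, and age-group tables are allowed. All of this stands and keeps the point small. It does not remove it. Grouping by visit and phase helps with follow-up length, but not with differences in age and sex within a group, and no growth standard is planned in any of these tables.

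Four stronger readings are tempting and should not be adopted:

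- **BMI will be computed on an outdated height, rising on treatment and falling at follow-up as if a drug effect had reversed.** No section carries height forward, and the general rules allow BMI from same-visit height only. The documented gap is a missing rule.
- **All subjects are observed for 64 weeks.** Only extension adolescents can be; children stop at 24 weeks after Day 1.
- **The sponsor regards growth as a known safety concern.** Protocol 2.2.1 discusses growth and skeletal development in animals, but reports no effect and concludes there is no age-related developmental concern.
- **Growth and drug effect cannot be separated at all.** That limit belongs to the planned summaries. Age, sex, height and weight are collected, so a more informative summary is available.

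**Conclusion.** The point holds as a low-cost improvement. The planned raw changes will mainly reflect normal growth, and the table as specified cannot separate this from a drug effect. Its size depends on assumed growth: at 1 to 7 cm/year, 0.5 to 3.6 cm by Day 169 and 1.3 to 9.0 cm by Day 449. The absence of a growth-standardised measure, of an untreated arm and of intermediate height measurements comes directly from the documents.

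On BMI, the finding is that the height rule is unspecified. The 1 to 9% overstatement at Week 48 shows why a rule is worth writing. It is conditional on a carry-forward that the SAP does not state, on a 155 cm starting height and on continuing growth.

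The consequence is limited to interpretation of a supportive safety table.

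**What to change.** In SAP 9.6.5:

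1. Add age- and sex-specific z-scores for height, weight and BMI, using a US growth reference and age at each measurement. All sites are in the United States (Protocol 3.2), and Protocol 2.4 already uses US body-weight data.
2. Summarise change in z-score from baseline by age group, alongside the raw values.
3. State that BMI is calculated only from screening height with screening weight and from final-visit height with final-visit weight. State also that baseline BMI is therefore the screening value, even though baseline weight is the Day 1 value.

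The cost is a little more programming and fewer BMI time points; the variables are already collected. Age at each measurement can be derived from date of birth where it is recorded, and otherwise approximated from age at consent and elapsed time. No extra height measurements or visit changes are needed. Z-scores reduce confounding by normal growth but do not replace a control group, and the report should say so.
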